**Table 11. Duration of Best Response from Start of First Mylotarg-Containing Line of Therapy, All Patients**

	L1 n=xx	L2 n= xx	L3 n=xx
No. of Events/No. of Patients	xxx/xxx	xxx/xxx	xxx/xxx
Median (months)	x.x	x.x	x.x
95% CI of Median	[x.x, x.x]	[x.x, x.x]	[x.x, x.x]

The time origin was the line of therapy in which Mylotarg treatment initiated.

**Figure 4. Kaplan-Meier Analysis of Duration of Best Response from Initiation of First Mylotarg-Containing Line of Therapy, First Mylotarg-Containing Line of Therapy, All Patients**

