    - b. Time to best response will be described for each regimen in the first qualifying Mylotarg-containing R/R-based line of therapy.
    - c. Duration of best response will be described for each regimen in the first qualifying Mylotarg-containing R/R-based line of therapy.

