- Duration of response for each regimen in the first qualifying Mylotarg-containing R/R-based line of therapy from the index date through the end of the third R/R-based line of therapy or the end of the record, whichever occurs first (Table 11).

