## 4. STATISTICAL METHODS

### 4.1. Endpoints

The primary study endpoints are effectiveness outcomes of rwEFS/rwRFS, rwOS, and response. Patient demographics and clinical characteristics, as well as treatment patterns will also be evaluated.

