Response will be assessed for the first and best overall response to treatment for each regimen in the first qualifying Mylotarg-containing R/R-based line of therapy during the study period. Response classifications will be made based on the treating physician's documentation of response itself, typically informed by radiological scan reports noted in the patient record. Classification is made to the following categories: complete response (CR), partial response (PR), stable disease (SD), progressive disease (PD), and not evaluable (NE), each based on the treating physician's statements. In cases where complete response with partial hematologic recovery (CRh), complete response with incomplete hematologic recovery (CRi), and morphologic leukemia-free state (MLFS) are explicitly included in the treating physician's statements, these additional classifications will be documented. The date of the best overall response for each regimen in the first qualifying Mylotarg-containing R/R-based line of therapy will be collected. Responses captured are based on treating physician's assessment in the medical record. Overall response rate will be defined as a percentage of patients whose best response is either CR, CRi, or MLFS, where available. Time to best response and duration of best response will be assessed using the descriptive techniques described above.

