**Table 12. Time to Best Response from Start of First Mylotarg-Containing Line of Therapy, All Patients**

	L1 n=xx	L2 n= xx	L3 n=xx
No. of Events/No. of Patients	xxx/xxx	xxx/xxx	xxx/xxx
Median (months)	x.x	x.x	x.x
95% CI of Median	[x.x, x.x]	[x.x, x.x]	[x.x, x.x]

The time origin was the line of therapy in which Mylotarg treatment initiated.

**Figure 5. Kaplan-Meier Analysis of Time to Best Response from Start of First Mylotarg-Containing Line of Therapy, All Patients**

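### SAP Table 11 and Figure 4 start the clock for duration of best response at the start of the Mylotarg line, so each duration also contains the time to best response

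*SAP*

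**What the plan says.** SAP section 4.1 puts response among the main endpoints: "The primary study endpoints are effectiveness outcomes of rwEFS/rwRFS, rwOS, and response". Objective 4 in SAP section 2 treats time to best response (4b) and duration of best response (4c) as separate measures. The second reads: "Duration of best response will be described for each regimen in the first qualifying Mylotarg-containing R/R-based line of therapy".

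The origin for duration appears only in the table shells of SAP section 7.4:

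- Table 11 title: "Duration of Best Response from Start of First Mylotarg-Containing Line of Therapy, All Patients".
- Table 11 footnote: "The time origin was the line of therapy in which Mylotarg treatment initiated".
- Figure 4 title: "Kaplan-Meier Analysis of Duration of Best Response from Initiation of First Mylotarg-Containing Line of Therapy".
- Table 12 title: "Time to Best Response from Start of First Mylotarg-Containing Line of Therapy, All Patients". Its footnote is identical to that of Table 11.

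The body text sets no origin. SAP 4.3.6 says "Time to best response and duration of best response will be assessed using the descriptive techniques described above". SAP 3.5.2 lists "Duration of response for each regimen in the first qualifying Mylotarg-containing R/R-based line of therapy from the index date", where the index date is the date of AML diagnosis. Protocol 9.3.4 and 9.7.6 are no more specific.

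**The concern.** A response has no duration before it exists. Duration of response should run from the date of the response to its loss. Table 11 and Figure 4 run it from the start of the treatment line, which is also the origin of Table 12. Time to best response is therefore reported once in Table 12 and again inside Table 11.

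The study is descriptive and makes no comparisons, so the reported median is itself the result and no comparator offsets the error. The error runs in one direction, towards longer apparent responses, and is proportionally largest when responses are short. Objective 4c would not be answered by the table meant to answer it.

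**Working it through.** **1. Which origins are stated.**

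| Place | Measure | Origin |
|---|---|---|
| SAP Table 11, title and footnote | Duration of best response | Start of first Mylotarg-containing line |
| SAP Figure 4, title | Duration of best response | Same |
| SAP Table 12, title and footnote | Time to best response | Same |
| SAP 4.3.6 | Both | None given |
| SAP 3.5.2; Protocol 9.3.4 | Duration of response | Window from the index date (diagnosis) |
| SAP 4.3.2 and 4.3.5 | rwEFS, rwRFS, rwOS; in 4.3.2 also duration of therapy | Given, but not for duration of response |

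The wording in 3.5.2 is probably a data window. Read as an origin, it would start the clock earlier still.

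**2. Identity.** Let S be line start, B the date of best response, and E the end of response or censoring. Then

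E − S = (B − S) + (E − B),

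so the Table 11 value equals the Table 12 value plus the duration counted from response. This holds for each responder, with or without censoring. If E is relapse or death, Table 11 comes close to rwRFS restricted to responders, but the visible text does not state that end event.

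**3. Size.** The plan has no figure to reproduce, because the shells hold placeholders. The illustration is anchored to the plan's own cycle length and treatment-failure windows. These are not data on response times.

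- Cycle: 21 days (SAP 4.2). 21 / 30.44 = 0.690 months.
- Three cycles (SAP 4.3.5 window): 2.070 months. Six cycles (Protocol 9.7.2 window): 4.139 months.
- If best response comes after 1 to 3 cycles, each duration is 0.7 to 2.1 months too long. At 6 cycles it is 4.1 months too long.

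Assume T = B − S is uniform on (a, b), D = E − B is exponential with median M, and there is no censoring. With λ = ln 2 / M, and when the median of T + D exceeds b,

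median(T + D) = M + (1/λ) · ln[(e^{λb} − e^{λa}) / (λ(b − a))].

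For M = 3, a = 0.690 and b = 2.070: λ = 0.2310; the ratio in brackets is (1.613 − 1.173) / 0.319 = 1.381; ln 1.381 = 0.323; 0.323 / 0.2310 = 1.40. The reported median is 4.40.

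| Assumed true median (months) | Reported, T over 1–3 cycles | Reported, T over 1–6 cycles |
|---|---|---|
| 3 | 4.40 (+47%) | 5.53 (+84%) |
| 6 | 7.39 (+23%) | 8.47 (+41%) |
| 12 | 13.38 (+12%) | 14.44 (+20%) |

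**4. Check under other assumptions.** A simulation used exponential durations with the same three medians and gamma-distributed times to best response with means of 1, 2 and 3 months. The overstatement ran from +8% (true median 12, mean time 1 month) to +107% (true median 3, mean time 3 months).

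**The case against.** The strongest reply is that the labels are template text and not a clock rule. The same footnote sits under Tables 6, 7, 8, 11 and 12, and it names a line, not a date. It is loose elsewhere too: SAP 4.3.5 starts rwRFS and rwOS at Mylotarg itself, while the footnotes to Tables 7 and 8 give the line. Table 10, a table of categories with no clock, has similar title wording. The title of Figure 4 repeats a phrase, which suggests pasting. SAP 4.3.6 collects the date of best response, and Objective 4 separates the two measures, so the authors may well have meant the response date. Sections 4.3.1 and 4.3.2 also contain redactions.

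Much of this is fair. The documents never name the response date as the origin, so this is a defect of specification and not a breach of a stated rule. Hidden text might supply an end event, a censoring rule or even an origin. The sizes are illustrative, and the larger column uses the protocol's 6-cycle window where the later SAP has 3. SAP 4.1 names response without naming duration; including duration is an inference from Objective 4.

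None of it removes the point. The footnote expressly states a time origin for a Kaplan-Meier median. It is the only visible operative instruction, and a program that follows it produces the wrong quantity. If the wording was pasted by accident, that is a reason to correct it.

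**Conclusion.** The concern holds. As written, Table 11 and Figure 4 report time from line start to the end of response, which overstates every responder's duration by that patient's time to best response. The direction follows from the identity and needs no assumption. The size does: about 1.4 months on the median if best response is spread evenly over 1 to 3 cycles of 21 days, and about 2.5 months over 1 to 6 cycles, with exponential durations and no censoring.

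This should be fixed, but the damage is confined to Objective 4c. Less certain, because of the redactions, is that Table 11 lacks an end event, a censoring rule and qualifying response categories. The visible text applies none to it, and its title says all patients.

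**What to change.** In SAP 4.3.6, define duration of best response as the time from the date of best response to relapse, progression or death, censored at last contact, among patients whose best response falls in a stated set of categories. If a redacted passage already sets the end event or censoring rule, refer to it from 4.3.6. Align SAP 3.5.2, the Table 11 title and footnote, and the Figure 4 title. Keep line start as the origin for Table 12.

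Two related points should be settled at the same time:

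- **Unit.** Objective 4c, 3.5.2 and 4.3.6 speak of each regimen; the Table 11 columns are lines. State which applies.
- **Abstraction window.** SAP 3.5.1.1 collects best response only through the first R/R-based line. Protocol 9.3.2 goes through the third, and SAP 4.3.6 needs the date for the first Mylotarg-containing line, whichever that is. Reconcile them so that the date exists for patients first given Mylotarg in line 2 or 3.

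**Cost.** One definition, a changed start date, a responder filter and new labels. Relapse/refractory, progression and death dates are already collected. If abstraction followed 3.5.1.1 literally, some line 2 and 3 charts need a second look, within a study of 20 to 30 patients.

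**Downside.** The medians rest on responders only. If 40% to 70% respond (assumed), that is 0.4 × 20 = 8 to 0.7 × 30 = 21 patients, or on average 2.7 to 7.0 per line column. Some medians or confidence limits may not be estimable.

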**Table 12. Time to Best Response from Start of First Mylotarg-Containing Line of Therapy, All Patients**

	L1 n=xx	L2 n= xx	L3 n=xx
No. of Events/No. of Patients	xxx/xxx	xxx/xxx	xxx/xxx
Median (months)	x.x	x.x	x.x
95% CI of Median	[x.x, x.x]	[x.x, x.x]	[x.x, x.x]

The time origin was the line of therapy in which Mylotarg treatment initiated.

**Figure 5. Kaplan-Meier Analysis of Time to Best Response from Start of First Mylotarg-Containing Line of Therapy, All Patients**

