#### 4.3.2. Time to Event Analysis

Single time to event analyses will be conducted as specified under the study objectives. CCI [REDACTED]

Real-world time to event outcomes in this study will include:

- rwEFS/rwRFS for the first 3 R/R-based lines of therapy. rwEFS will be defined as the time from the treatment initiation date (for the first agent in the first regimen in the first line of Mylotarg-containing therapy) to the date of treatment failure (TF), relapse from Complete Response (CR) or better, or death from any cause, whichever comes first. TF is defined as failure to achieve CR or better following up to 3 cycles of Mylotarg. rwRFS will be defined as the time from the treatment initiation date (for the first agent in the first regimen in the first line of therapy) to the date of a relapse event, or death from any cause, whichever comes first.
- rwOS, from the first line of therapy through the end of record or death, whichever occurs first, and
- Duration of therapy across lines of therapy from the first line of therapy through the third R/R-based line of therapy.

The time origin for analysis of rwEFS/rwRFS is the start of therapy within each specific line of therapy, and the terminal event is the earlier of an R/R event or death. The time origin for analysis of rwOS is the start of therapy within the first line of therapy, and the terminal event is death. Patients who are not indicated to be deceased at last known contact (patients who are alive, or lost to follow-up) will be censored. The time origin for analysis of duration of therapy is start of Mylotarg, and the terminal event is discontinuation of that therapy.

#### 4.3.3. Methods under Objective 1

*Objective 1: To describe the demographic and clinical characteristics as outlined in the variable list below for patients diagnosed with AML who received Mylotarg in a real-world setting.*

Descriptive analysis as detailed in [Section 4.3.1](#) will be conducted for work under this objective. Demographic characteristics that will be reported will include sex, patient age, race/ethnicity, height, weight, BMI, insurance status, and region of residence closest to the index date. Clinical characteristics that will be reported will include comorbidities and comorbidity index score, ECOG score, and disease characteristics, such as stage at index date, cytogenetic testing at index date, and whether the AML diagnosis was de novo versus secondary.

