rwEFS will be defined as the time from the treatment initiation date (for the first line of Mylotarg-containing therapy) to the date of treatment failure (TF), relapse from CR or better, or death from any cause, whichever comes first. TF is defined as failure to achieve CR or better following up to 3 cycles of Mylotarg. Accordingly, the time origin for rwEFS will be the start of Mylotarg in the first line of therapy in which it is used. The terminal event for analysis of rwEFS is the earlier of treatment failure, relapse from CR or better (as evidenced by provider documentation), or death. Patients who have not died or experienced an event by the date of last contact within the medical record will be censored for analysis of rwEFS.

rwRFS will be defined as the time from the treatment initiation date (during the first line of Mylotarg-containing therapy) to the date of a relapse event, or death from any cause, whichever comes first. The time origin for rwRFS will be the start of Mylotarg in the first line of therapy in which it is used. The terminal event for analysis of rwRFS will be the earlier of a relapse event (as evidenced by provider documentation), or death. Patients who have not died or experienced a relapse event by the date of last contact within the medical record will be censored for analysis of rwRFS.

The time origin of rwOS analysis is the start of the first Mylotarg use. The terminal event for analysis of rwOS is date of death. Note that Social Security Disability Insurance (SSDI) records have an expected lag of up to 4 months. Accordingly, patients who are not indicated to be deceased in clinical records or SSDI records will be censored for rwOS analysis as of the later of 1) the latest date known alive within the clinical record, 2) 4 months prior to the date of most recent SSDI update.

Separate Kaplan-Meier analyses will be conducted for each rwEFS, rwRFS and rwOS endpoint.

#### 4.3.6. Methods under Objective 4

*Objective 4: To evaluate response among AML patients who received Mylotarg in a real-world setting.*

- a. First and best response for each regimen in the first qualifying Mylotarg-containing R/R-based line of therapy.
- b. Time to best response for each regimen in the first qualifying Mylotarg-containing R/R-based line of therapy.
- c. Duration of best response for each regimen in the first qualifying Mylotarg-containing R/R-based line of therapy.

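### SAP Table 12 and Figure 5 plan Kaplan-Meier for time to best response without defining event, risk set or handling of failure and death; the usual implementation would overstate response

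*SAP*

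**What the plan says.** The shells and the methods text of the SAP do not match.

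- **Shells (SAP 7.4).** Table 12 is titled "Time to Best Response from Start of First Mylotarg-Containing Line of Therapy, All Patients". Its rows are "No. of Events/No. of Patients", a median in months and a 95% CI of the median, in columns for lines 1, 2 and 3. The footnote reads "The time origin was the line of therapy in which Mylotarg treatment initiated". Figure 5 is titled "Kaplan-Meier Analysis of Time to Best Response from Start of First Mylotarg-Containing Line of Therapy, All Patients".
- **Methods text (SAP 4.3.6; the protocol has the same sentence in 9.7.6).** "Time to best response and duration of best response will be assessed using the descriptive techniques described above". The techniques listed in SAP 4.3.1 are means, standard deviations, quartiles, medians and ranges.
- **Where Kaplan-Meier is specified (SAP 4.3.5).** "Separate Kaplan-Meier analyses will be conducted for each rwEFS, rwRFS and rwOS endpoint". Time to best response is not among the time-to-event outcomes listed in SAP 4.3.2.
- **Censoring.** The nearest general rule, in SAP 4.3.2, stands with rwOS: "Patients who are not indicated to be deceased at last known contact (patients who are alive, or lost to follow-up) will be censored". SAP 4.3.5 adds rules for rwEFS, rwRFS and rwOS. None is given for time to best response.
- **Event.** SAP 4.3.6 allows best response to be CR, PR, SD, PD or NE, with CRh, CRi and MLFS where documented. It does not say which categories count as an event in Table 12. The derived-variable entry for time to best response in SAP 3.5.2 points to Tables 9–11 and 14–15, not to Table 12.

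**The concern.** A line of therapy can end without a response. The patient may die, prove refractory, progress or move to the next line, and from then on cannot respond to that line. These are competing events. The SAP's own background (Section 1) puts complete remission after induction at 60%–70%, so 30%–40% without it, and patients may also enter in second or third line.

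Ordinary Kaplan-Meier has only events and censored times. If a patient who fails or dies is censored at that moment, the estimator assumes that this patient would later have responded at the same rate as those still at risk. The curve then rises above the proportion who actually respond.

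At stake is the answer to Objective 4b. SAP 4.1 names response among the primary study endpoints. As written, the programmer has two instructions that do not agree, and each open reading of the shell gives a different number. The choice should be made before results are seen.

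**Working it through.** The documents give no figure for this analysis, so there is none to reproduce. The check takes the direction first, then an illustrative size.

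**1. Direction.** Let h1 be the hazard of response and h2 that of failure or death without response, with cumulative hazards H1 and H2.

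- Cumulative incidence: CIF(t) = ∫ h1(u)·exp(−H1(u) − H2(u)) du.
- Kaplan-Meier with failures censored when they occur: 1−KM(t) = ∫ h1(u)·exp(−H1(u)) du.

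Since exp(−H1) ≥ exp(−H1 − H2), 1−KM is never below CIF, and its median is never later. This needs no distributional assumption.

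**2. Size under assumed gamma times.** A fraction p responds, with time to response gamma (shape 4, mean 1.5 months, median 1.4). The rest fail or die at gamma times (shape 2, mean 2.0 months). There is no other censoring. All of these are assumptions.

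- CIF(t) = p·F1(t), with F1(3) = 0.9576.
- 1−KM(t) = 1 − exp(−∫ p·f1/[p·S1 + (1−p)·S2] du), integrated numerically.
- The CIF median is the time at which F1 = 0.5/p, and exists only for p above 0.5.

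| p | 1−KM at 3 mo | CIF at 3 mo | Excess (points) | KM median (mo) | CIF median (mo) |
|---|---|---|---|---|---|
| 40% | 56.7% | 38.3% | 18.4 | 2.47 | not reached |
| 50% | 66.6% | 47.9% | 18.7 | 2.05 | approached, never crossed |
| 60% | 75.0% | 57.5% | 17.5 | 1.81 | 2.19 |
| 70% | 82.0% | 67.0% | 14.9 | 1.65 | 1.82 |

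(Excess is taken from unrounded values.) At 40%, Kaplan-Meier gives a median of about 2.5 months although fewer than half of the patients ever respond.

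**3. Sensitivity with constant hazards.** Assume a mean of 1.5 months to the first of response or failure. At 6 months, 1−KM = 1 − exp(−4p) and CIF = p·(1 − exp(−4)).

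- p = 0.45: 83.5% against 44.2%. KM median 1.5·ln 2/0.45 = 2.31 months; CIF median not reached.
- p = 0.60: 90.9% against 58.9%. KM median 1.5·ln 2/0.60 = 1.73 months; CIF median −1.5·ln(1 − 0.5/0.60) = 2.69 months.
- p = 0.65: 92.6% against 63.8%.

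The direction is the same and the gap is larger, so the size depends on the assumed hazards.

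**4. Planned sample size.** With n = 25 (the plan expects 20–30), p = 0.65, the constant hazards above and assumed follow-up uniform on 6–30 months, 2,000 simulated studies gave a Kaplan-Meier curve ending at 0.95 on average, against a true 0.65. The typical median was 1.59 months, against 2.19 when non-responders stay in the risk set.

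**The case against.** A reader might infer that the SAP prescribes censoring at failure or death, so that the bias is built in. The documents do not support that. No section sets the event, risk set or censoring rule for Table 12 or Figure 5, and other readings are open:

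- **Responders only.** The all-patients label may mean the main cohort, unstratified, as opposed to the ad-hoc subset. Table 11 carries the same label for duration of best response, which cannot be measured in someone who never responded. With responders only, the bias does not arise; the constant-hazard median is 1.5·ln 2 = 1.04 months.
- **Non-responders kept at risk to the end of potential follow-up.** This reproduces the cumulative incidence.
- **Any best-response category counted as an event, including SD and PD.** This is a different quantity, with a curve near 1.

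That part of the objection stands: the bias is conditional. But no section chooses one of these readings, and a row of events over patients suggests that some patients are expected to have no event. Censoring non-responders at failure or death is what a standard program would do with this shell.

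The second objection is low stakes: a descriptive study with no comparisons and 20–30 patients split over three lines. At a 60% response rate the approximate 95% half-width for a proportion is 1.96·√(0.24/n), about 21 points at n = 20 and 18 at n = 30, before any split. This limits the consequence. It does not excuse a systematic error that could be of similar size and that the printed CI would not reveal.

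**Conclusion.** The point holds in conditional form. What the documents establish is that the shell and SAP 4.3.6 disagree on method, and that event, risk set and handling of non-response are undefined. If patients are censored when they fail or die, the curve overstates response and the median is too early relative to cumulative incidence. Under the assumed gamma times the excess at 3 months is about 15–19 points for response rates of 40%–70%. Those sizes rest on assumed times and response rates that the plan does not give; only the direction is general.

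Two further inferences should not be drawn. A reader might expect Figure 5 to contradict the ORR in Table 10. That depends on the unstated censoring rule, and because the event is undefined the two could differ under any estimator. A reader might also take SAP 4.3.6 to restrict the summary to responders. It names descriptive techniques only, so the restriction proposed below is a recommendation, not something the SAP already requires.

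**What to change.** 1. **Define the event.** State which best-response categories count, using one reconciled ORR definition. SAP 4.3.6 lists CR, CRi or MLFS, while the footnotes to Tables 9 and 10 list CR, CRh or CRi.
2. **Table 12.** Report n, median, quartiles, minimum and maximum of time to best response among responders, and label the table as responders only. This fits the descriptive techniques of SAP 4.3.1.
3. **Figure 5.** Replace it with an Aalen-Johansen cumulative incidence curve in all patients in the line, with death, R/R event or disease progression, or start of the next line without response as competing events. Censor only patients still able to respond at last contact.
4. **SAP 4.3.6.** Add a sentence stating both methods, so that text and shells agree.

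The cost is a shell edit and a standard procedure. The dates needed are already collected: R/R events and progressions under SAP 3.5.1.1, treatments and death under 3.5.1.2, and best response under 4.3.6. The drawback is that with 20–30 patients the cumulative incidence curve will be imprecise, more so if shown by line.
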